4.4 STATISTICAL POWER AND DESIGN

The MRI Study will employ a 2 (psychopathy: high vs. low) x 2 (empathy-type: antisocial vs. prosocial) mixed-effects design. The outcome variables are pain ratings and brain activity during such pain ratings. G*Power statistical software (version 3.1) was used to conduct power analyses for this interactive effect, revealing that such a moderation model will have at least 80% power to detect a modest interactive effect size estimate of $f = .08$ with 36 participants, 18 per group.

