4.1 BRIEF SUMMARY

Aggressive behaviors inflict massive costs on the public health. Psychopathy — the tendency to be callous, manipulative, and lack remorse — is one of the most central predictors of aggression and a core feature of psychopathology. Psychopathic individuals' antisocial acts have long been thought to be due to an inability to empathize with their victims. However, recent work suggests that psychopathic individuals have intact empathic abilities. Instead of employing their empathy to help others, psychopathic individuals appear to use empathy to exact greater harm on their victims. Such *antisocial empathy*, its neural bases, and its effects on the aggression of psychopathic individuals remains unexamined. We propose a functional neuroimaging study in which we will recruit 36 healthy adult male participants, who are at the low and high extremes of the psychopathy distribution (18 per group). While undergoing functional MRI, participants will complete a psychological task that evokes antisocially- and prosocially-motivated empathic responding. We predict that psychopathic individuals will exhibit greater recruitment of the brain's cognitive empathy network when empathy facilitates antisocial goals (i.e., harming a competitor) and that this neural recruitment will predict greater aggression towards their targets. These findings will serve as an initial foray into this potential new frontier for research on psychopathy, empathy, and aggression. If supported, this novel approach would readily translate into new motivation-focused interventions and would inform biological and psychological models of the monumentally-costly phenomenon of psychopathic aggression.

4.2.a NARRATIVE STUDY DESCRIPTION

Aggressive behavior is a substantial public health concern in the United States, with approximately 1.2 million violent crimes occurring in 2015¹. Such violent crimes (e.g., aggravated assault, murder, rape) resulted in over 1.5 million non-fatal injuries and over 17,000 deaths in 2015². Psychopathy is a well-established risk factor for such violence. Understanding the psychological factors (such as antisocial empathy) that explain such psychopathic aggression), as well as the neural mechanisms that transmit these effects, is crucial to developing effective and targeted psychological and pharmacological interventions that seek to reduce such violent outcomes. This project will empirically investigate these phenomena.

4.2.b PRIMARY PURPOSE

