4.3 OUTCOME MEASURES

Primary - Change in accuracy of empathic pain judgments

Time frame: collected during intervention.

Brief description: Accuracy rates for pain ratings of faces during antisocial empathy trials (as compared to prosocial empathy trials).

NIH-Defined Phase III Clinical Trials: N/A

Primary - Change in brain activity assessed by fMRI

Time frame: collected during intervention.

Brief description: Blood-Oxygen-Level-Dependent signal change (as assessed by functional MRI) in the cognitive empathy brain network during antisocial empathy trials (as compared to prosocial empathy trials).

NIH-Defined Phase III Clinical Trials: N/A

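### Does the group by empathy-type interaction need pre-specified simple effects before it can support the antisocial-empathy hypothesis?

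*Combined protocol and SAP*

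**What the plan says.** Section 4.4 describes a "2 (psychopathy: high vs. low) x 2 (empathy-type: antisocial vs. prosocial) mixed-effects design" with 18 participants per group. It states "at least 80% power to detect a modest interactive effect size estimate of" f = .08. The interaction is the only effect with a stated power basis.

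Section 4.3 lists two primary outcomes, each a comparison of trial types. The behavioural one is "Accuracy rates for pain ratings of faces during antisocial empathy trials (as compared to prosocial empathy trials"). The imaging one is BOLD signal change "in the cognitive empathy brain network during antisocial empathy trials (as compared to prosocial empathy trials").

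Section 4.1 gives the scientific prediction: psychopathic participants will make more use of the "cognitive empathy network when empathy facilitates antisocial goals". It sets this against the older view that their conduct reflects "an inability to empathize with their victims", and offers a motive account instead: "Instead of employing their empathy to help others, psychopathic individuals appear to use empathy to exact greater harm on their victims". It also predicts that "this neural recruitment will predict greater aggression towards their targets", but Sections 4.3 and 4.4 give no aggression outcome or analysis.

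No section names a contrast of high against low within either trial type, or says how a significant interaction is to be worded.

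**The concern.** The prediction in Section 4.1 can be read as a statement about one cell of the design: high-psychopathy participants respond more than low-psychopathy participants on antisocial trials. The interaction is a difference of differences and does not show which cell moved. It could be significant because the high group rises on antisocial trials, because it falls on prosocial trials, or because it falls on both but further on prosocial trials.

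On that reading, a significant result could be reported as heightened antisocial empathy when the high group shows no rise on antisocial trials, or even a fall. Follow-up contrasts chosen after seeing the data, across two primary outcomes, would leave room for selection in how the finding is explained.

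**Working it through.** **Inputs.** From Section 4.4: N = 36, 18 per group, f = .08, power of at least 80%. Not stated: alpha, the within-person correlation ρ and the number of measurements m. Assumed here: two-sided .05, m = 2, SD 1 in each condition, and ρ as shown. Effect sizes other than f = .08 are also assumed.

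**1. The plan's power figure.** For a within-between interaction, λ = f²·N·m/(1 − ρ) on 1 and 34 df. Here f²·N·m = .0064 × 36 × 2 = 0.4608.

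- ρ = .5: λ = 0.4608/.5 = 0.92, power 15%.
- ρ = .945: λ = 0.4608/.055 = 8.4, power 80%.

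The stated 80% therefore needs ρ of about .945 with two measurements, or about 82 measurements at ρ = .5. The plan states neither ρ nor m, so the figure is not reproduced at ordinary settings but is not shown to be wrong. The algebra in step 2 does not depend on it.

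**2. What the interaction identifies.** Write H and L for the high and low groups, A and P for antisocial and prosocial trials:

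I = (HA − HP) − (LA − LP) = (HA − LA) − (HP − LP).

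| Pattern (cells not mentioned are 0) | I | High − low, antisocial | High − low, prosocial |
|---|---|---|---|
| High group +1 on antisocial only | 1 | 1 | 0 |
| High group −1 on prosocial only | 1 | 0 | −1 |
| High group +0.5 and −0.5 | 1 | 0.5 | −0.5 |
| Low group −1 on antisocial, high group flat | 1 | 1 | 0 |

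The interaction cannot separate these patterns. The simple effects cannot separate the first from the last.

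**3. How often the interaction is significant in the predicted direction.** The table rests on 100,000 simulated trials per row, ρ = .5, with a t test on difference scores (34 df). Analytic check: the SD of a difference is √(2(1 − .5)) = 1, so a 0.96 SD shift has noncentrality 0.96 × √(18/2) = 2.88, which gives 80% power.

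| High − low shift, antisocial / prosocial | Interaction significant |
|---|---|
| +0.96 / 0 | 79.8% |
| 0 / −0.96 | 79.9% |
| +0.48 / −0.48 | 79.8% |
| −0.48 / −1.44 | 79.9% |
| −0.96 / −0.96 | 2.5% |

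In the fourth row the antisocial response is also significantly lower in 18.0% of trials. The last row is the general-deficit view that Section 4.1 argues against; it produces the interaction only at chance level. So the planned test does discriminate against that rival.

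**4. Test against outcome.** Section 4.3 defines each primary outcome as antisocial relative to prosocial. Comparing that quantity between groups is exactly I. The test and the defined outcome agree.

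**5. What fixed simple-effect rules would add.** A 95% interval for one simple effect has half-width 2.032 × √(2/18) = 0.68 SD. At the plan's f = .08 the whole contrast is 4 × .08 = 0.32 SD. If all of it lies on antisocial trials, that simple effect has about 15% power, and 80% would need about 154 per group.

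Suppose a wording rule lets an antisocial increase be claimed only when its simple effect is significant.

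- f = .08, ρ of about .945, whole effect on antisocial trials: the interaction is significant in 79.9% of trials. The increase can be claimed in 13.2%, and the source is left unresolved in 64.4%.
- Even split (+0.48 / −0.48), ρ = .5: only the antisocial effect is significant in about .236 of trials and only the prosocial in about .235. Then (.236 + .235)/.80 = 59% of significant interactions get a one-sided label although both trial types contribute equally.

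**The case for a change.** The strongest case for a change is the pattern in which the high group is lower on both trial types. The planned test then succeeds in 80% of trials while the response is reduced on the very trials where Section 4.1 can be read as predicting an increase. Section 4.1 also hopes that support will lead to interventions aimed at motivation, and for that it matters whether antisocial empathy is raised or prosocial empathy lowered. Two contrasts per outcome would cost little and take no power from the interaction. The aggression prediction does not settle the matter, since it has no stated analysis and would not show which trial type drives the difference.

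Part of this stands. A significant interaction does not by itself locate the effect, and a report that treated it as proof of an absolute antisocial increase would overreach. The case for amending the plan is weaker:

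- The antisocial-cell reading of Section 4.1 is possible but not compelled. The motive account speaks of empathy being put to a different use, so a fall confined to prosocial trials partly fits it.
- The lower-on-both example rests on an assumed 1.44 SD prosocial deficit, which sits badly with Section 4.1's premise that empathic ability is preserved.
- Between-group contrasts within one trial type lose the within-person control, so general group differences in signal can enter them. For BOLD they would also need a reference baseline, which the document does not describe.
- With only the two extremes of psychopathy recruited, a high-minus-low difference on antisocial trials could still reflect the low group.

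**Conclusion.** No change to the plan follows. The interaction validly tests both primary outcomes as Section 4.3 defines them, and no passage promises a conclusion about antisocial trials alone. What is missing is a description of routine follow-up, which a competent analyst supplies: four cell means and the high-minus-low difference on each trial type with 95% intervals, with a significant interaction described as a relative shift unless those intervals support more.

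The algebra holds whatever the effect size. The frequencies (about 80% under either explanation, 59% one-sided labels under an even split) assume SD 1, ρ = .5, two-sided .05 and shifts totalling 0.96 SD. The 0.68 SD half-width depends only on 18 per group and the 95% level. At that precision, stricter pre-specified labelling would seldom settle the source of a small effect and would often misattribute a shared one.

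### The 80% power claimed for f = .08 with 36 participants cannot be reproduced for the 2x2 interaction; at alpha .05 it needs an undocumented between-condition correlation of about .945

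*Combined protocol and SAP*

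**What the plan says.** Section 4.4 describes a "2 (psychopathy: high vs. low) x 2 (empathy-type: antisocial vs. prosocial) mixed-effects design". Section 4.2.e makes empathy type a within-participant factor, so the design has two groups and two repeated conditions. The section reports that G*Power 3.1 was used for the interaction and claims "at least 80% power to detect a modest interactive effect size estimate of $f = .08$ with 36 participants, 18 per group". It applies this one figure to two outcomes: "The outcome variables are pain ratings and brain activity during such pain ratings". Section 4.3 lists both as primary, each as a contrast of antisocial with prosocial trials.

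Neither section 4.4 nor any other supplied section gives alpha, the correlation between the two conditions, the number of measurements entered in G*Power, or which of the software's effect-size conventions was used. The documents contain no other justification for the sample size.

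**The concern.** An f of .08 is a small standardised effect, and 18 per group is a small sample. In a within-between interaction test the two can be reconciled only if the repeated scores are very highly correlated, because the test works on each participant's difference score and a high correlation shrinks the variance of that score. The plan does not say that such a correlation was assumed, or give a reason to expect one.

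What is at stake is how the result will be read. Someone who takes section 4.4 at face value would treat a null interaction as evidence against even a modest effect. If the true sensitivity is several times coarser, a null result would leave interactions of that size open.

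**Working it through.** **Inputs from the documents.** N = 36, 18 per group; k = 2 groups; m = 2 conditions; f = .08; target power at least 80% (sections 4.2.e and 4.4).

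**Inputs assumed.** Two-sided alpha .05, with .025 and .10 also shown. Correlation rho between conditions from 0 to .9. No dropout or unusable scans, which is the most favourable case.

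**Formula.** For the repeated-measures within-between interaction, power comes from a noncentral F distribution with

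- lambda = f² × N × m / (1 − rho) = .0064 × 72 / (1 − rho) = .4608 / (1 − rho)
- df1 = (k − 1)(m − 1) = 1 and df2 = (N − k)(m − 1) = 34.

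**Step 1: attempt the plan's own figure (alpha .05).** The last column is the f that would have 80% power.

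| rho | lambda | power at f = .08 | f detectable with 80% power |
|---|---|---|---|
| 0 | 0.461 | 10% | .34 |
| .3 | 0.658 | 12% | .28 |
| .5 | 0.922 | 15% | .24 |
| .7 | 1.536 | 23% | .19 |
| .8 | 2.304 | 31% | .15 |
| .9 | 4.608 | 55% | .11 |

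None of these rows reaches 80%. The detectable f runs from about 4.3 times the printed value down to about 1.3 times. A simulation with 40,000 runs agrees: power .126, .153, .224 and .547 at rho .3, .5, .7 and .9.

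**Step 2: the correlation the claim requires.** Power of 80% with df (1, 34) needs lambda = 8.317, so rho = 1 − .4608 / 8.317 = .945. At alpha .10 (equivalent to a one-sided .05 test) lambda is 6.439 and rho is .928. At alpha .025 lambda is 10.256 and rho is .955. The choice of alpha therefore does not explain the figure.

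**Step 3: the same result without rho.** In the 2x2 design, f corresponds to a group difference of 4f SD in the antisocial-minus-prosocial change, here .32 SD. The SD of that change is √(2(1 − rho)). With d as the ratio of the two, lambda = 9d². So d = √(8.317 / 9) = 0.96 for 80% power at any correlation (0.85 at alpha .10, 1.07 at alpha .025). On that scale the printed f = .08 is .32 / √1.4 = 0.27 at rho .3, .32 / 1 = 0.32 at rho .5, and .32 / √.6 = 0.41 at rho .7.

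**Step 4: other readings of .08.**

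- As f² (f = √.08 = .283): power is 79.6% at rho .3 and 91% at rho .5. It reaches 80% from rho of about .31.
- As eta² (f = √(.08 / .92) = .295): power is 83% at rho .3 and 93% at rho .5. It reaches 80% from rho of about .25.
- As f, with individual trials entered as measurements: 6 measurements at rho .9 give 82%, while 40 at rho .5 give 55%. The numerator df is then m − 1, so this is not the stated 2x2 test, and no trial count is given.
- As f in the partial-eta-squared convention, or in a between-subjects ANOVA on 36 participants or 72 observations: 7% to 10%.

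A mislabelled f² or eta² would bring the claimed power within reach at a moderate correlation. The detectable f would then be .283 / .08 = 3.5 or .295 / .08 = 3.7 times what is printed.

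**The case against.** The strongest reply is that this shows missing inputs rather than a proven error. A correlation of .945 does deliver 80%, and nothing in the documents contradicts that value. That is right: the claim is not impossible. But the printed effect size then rests entirely on an extreme value that the plan neither states nor supports.

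A second reply is that a trial-level mixed model keeps the interaction at one degree of freedom. If f = .08 is scaled to the SD of single trials, with a random intercept and no person-specific condition effect, power is about 84% with 10 trials per condition at a correlation of .5 (lambda = .4608 × 10 / .5 = 9.2). This is a fair limit on the .945 figure, which applies when f is scaled to the SD of each participant's condition score. However, the documents give no trial count or variance model, person-specific condition effects would lower the power, and this is not G*Power's repeated-measures calculation. It also leaves the 0.96 SD result unchanged.

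Three smaller points stand. Two conditions can be read from the design, so what is missing is the number entered in the software. The f² and eta² readings are conjecture. Using one power figure for two outcomes is not itself an error, although their correlations may differ.

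**Conclusion.** The concern holds. As printed, the power statement cannot be reproduced for the stated 2x2 interaction. With f scaled to condition scores and two-sided alpha .05, power at f = .08 is 10% to 55% for correlations from 0 to .9, and 80% requires about .945. The least assumption-dependent statement is that 18 against 18 has 80% power for a group difference of about 0.96 SD in the difference score. It depends on alpha and on complete data, but not on the correlation.

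Which explanation applies (a very high correlation, a mislabelled effect size, or trials entered as measurements) cannot be settled from the documents; the sponsor's G*Power inputs would settle it. Because this is the only sample-size justification, it must be corrected.

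**What to change.** Keep N = 36 and revise section 4.4 as follows.

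- State alpha and sidedness, the number of measurements entered, the G*Power procedure and its effect-size convention.
- State the assumed between-condition correlation, with its source, separately for pain-rating accuracy and for brain activity.
- If .08 was f² or eta², print it as such.
- Otherwise replace it with the detectable effect under the stated inputs. For example: f = .24 at an assumed correlation of .5 (.28 to .19 for correlations of .3 to .7), two-sided alpha .05, equal to a 0.96 SD group difference in the antisocial-minus-prosocial contrast.
- Add that a null result does not exclude interactions smaller than the stated detectable effect.

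The cost is a few sentences in one section. No participants are added and neither the design nor the analysis changes, but the stated sensitivity becomes less favourable.

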4.5 SUBJECT PARTICIPATION DURATION

Participation in our study consists of a single, 3-hour laboratory session.

4.5 FDA-REGULATED INTERVENTION?

No

4.7 DISSEMINATION PLAN

The PI, [name], has submitted this study as a clinical trial on ClinicalTrials.gov immediately after notification of the award (ID: NCT03974282). It is currently under review. As per the NIH Policy on the Dissemination of NIH-Funded Clinical Trial Information, the PI will report summary results of this study to ClinicalTrials.gov within the timelines specified by this policy. The Clinical Research Compliance Program at Virginia Commonwealth University has and will assist [name] with these aforementioned steps and ensure that compliance is maintained with NIH dissemination policies and Virginia Commonwealth's own internal clinical trial dissemination policy.
